#### H3B-6527

The NCT02834780 study [16] was the first-in-human clinical trial of H3B-6527, a multicenter, non-randomized, open-label, single-agent, single-arm, phase I study that planned to enroll 128 subjects (128 subjects were enrolled actually) and aimed to assess the safety, tolerability, PK, pharmacodynamics, and preliminary antitumor activity of H3B-6527 in subjects with HCC or intrahepatic cholangiocarcinoma (ICC). The trial used a 3+3 design with dose escalation ranging from 300 to 2000 mg QD or 500 to 700 mg twice daily (BID). So far, 128 subjects have been enrolled in the study, of whom 90 FGF19-positive HCC subjects were treated (48 QD, 42 BID), and ICC subjects (38 subjects have been enrolled actually) were suspended due to limited efficacy. No DLT was observed, and no treatment-related grade 4-5 AEs were observed. Based on the safety, efficacy and PK data, the RP2D of H3B-6527 was 1000 mg QD. In the QD administration group, 12.5% subjects experienced grade 3 AEs, and 62.5% subjects experienced treatment-related AEs, the most common of which were diarrhea (45.8%), asthenia (12.5%), and nausea (12.5%). The incidence of discontinuation due to AEs in the QD administration group was 8.3%. The interim data analysis showed that for HCC subjects who had previously received >2 lines of therapy, the overall survival (OS) of QD administration was 10.6 months, the progression-free survival (PFS)

was 4.1 months, the overall response rate was 16.7 % (both PR), and the clinical benefit rate was 45.8% (response + stable disease for >17 weeks). The existing results have shown that H3B-6527 has good tolerability and anti-HCC activity.

#### 1.4 BB102 Introduction

Generic name: BB102 tablets

Other code: None

**English chemical name:** N-(5-cyano-4-((2-methoxyethyl) amino) 56yridine-2-yl)-7-formyl-6-((4-methyl-2-oxopiperazin-1-yl)methyl)-3,4-dihydro-2,4-methano-1,8-naphthyridine-1(2H)-carboxamide 2-hydroxypropane-1,2,3-tricarboxylate

**Molecular formula:** C26H30N8O4·C6H8O7

**Molecular weight:** 710.70

Stereochemistry: None

BB102 is a small molecule FGFR4 inhibitor independently developed by the sponsor. It has the same mechanism of action as BLU-554 and FGF401, and belongs to the innovative drug/molecular.

The dosage, route of administration, method of administration and treatment schedule of the investigational product (BB102 tablets) are detailed in Sections 5.2 and 6.2.

# 1.5 Summary of Nonclinical Studies of BB102

Nonclinical studies have shown that BB102, as a novel FGFR4 inhibitor with completely independent intellectual property rights, has a clear mechanism of action, high pharmacodynamic target selectivity, and high activity *in vitro* and *in vivo*, can significantly inhibit the growth of various liver cancer, rhabdomyosarcoma, and breast cancer xenograft models, and has good safety. BB102 is expected to be characterized by few adverse effects, low effective dose, and long duration of drug effect in clinical applications.

The results of nonclinical studies are detailed in the Investigator's Brochure. This protocol only provides a brief description.

# 1.5.1 Pharmacology

#### **Primary Pharmacodynamics**

The study of compounds effects on FGFR4 kinase detected the inhibitory activity of BLU-554 and BB102 on FGFR4, and the half maximal inhibitory concentration (IC50) of BLU-554 and BB102 were 13.94 nM and 2.522 nM, respectively, showing strong inhibitory effects. Compared with BLU-554, BB102 has higher inhibitory activity on FGFR4. The study of inhibitory effect of BB102 on the FGF19/FGFR4-mediated signal pathway in human hepatocellular

carcinoma Hep 3B cells showed that BB102 completely inhibited ERK and AKT protein phosphorylation which is downstream of FGF19/FGFR4 in human hepatocellular carcinoma cell Hep 3B even at 16.7 nM, and its inhibitory potency was similar to FGF401 and stronger than BLU-554. It was demonstrated that BB102 inhibited the growth of hepatocellular carcinoma Hep 3B cells by selectively inhibiting the kinase activity of FGFR4, thereby inhibiting its downstream ERK/AKT signal pathway.

The study of inhibitory activity on cell proliferation showed that BB102 had a strong inhibitory effect on the proliferation of FGF19/FGFR4 high-expressing tumor cells, such as human hepatocellular carcinoma cells Hep 3B, HuH-7 and JHH-7, human breast cancer cell MDA-MB-453, and human rhabdomyosarcoma cell SJCRH30. The inhibitory effect of BB102 on Hep 3B, HuH-7 and JHH-7 was IC50 = 5.8 nM, 8.7 nM and 21.760 nM, respectively, which was better than the positive control BLU-554 (IC50 = 23.7 nM, 30.7 nM and 87.980 nM), and slightly worse than the positive control FGF401 (IC50 = 2.3 nM, 3.2 nM and 10.810 nM). The IC50 of BB102 on SJCRH30 was 1.9 nM, which was better than that of positive control BLU-554 (IC50 = 5.2 nM) and slightly worse than that of positive control FGF401 (IC50 = 0.6 nM). The IC50 of BB102 on MDA-MB-453 was 24.7 nM, which was slightly worse than that of positive control FGF401 and BLU-554 (IC50 = 9.5 nM and 6.6 nM). **In addition,** BB102 also had a strong inhibitory effect on the proliferation of Ba/F3 cell lines with FGFR4V550L or FGFR4N535K mutation (IC50 = 0.045 μM and 0.023 μM, respectively), which was better than the positive control BLU-554 (IC50 = 0.572 μM and 0.206 μM, respectively).

In the *in vivo* pharmacodynamic study, five FGF19/FGFR4 high-expressing xenograft models were selected: human hepatocellular carcinoma cells Hep 3B, HuH-7 and JHH-7, human breast cancer cell MDA-MB-453, and human rhabdomyosarcoma cell SJCRH30. The study of "Inhibitory Effect of BB102 on the Growth of Subcutaneous Xenografts of Human Hepatocellular Carcinoma HuH-7 cells in Balb/c nude Mice" consisted of 7 groups, including the vehicle control group (BID, 21 days), the positive control sorafenib 60 mg/kg group (QD, 21 days), the positive control BLU-554 30 mg/kg group (BID, 21 days), positive control BB181 (FGF401 citrate) 30 mg/kg group (BID, 21 days), BB102-citrate 30 mg/kg group (BID, 21 days), BB102-citrate 60 mg/kg group (BID, 21 days), BB102-citrate 90 mg/kg group (BID, 7 days; QD, 14 days). On Day 20 after treatment, compared with the vehicle control group, BB102-citrate had a significant antitumor effect at doses of 30 mg/kg, 60 mg/kg and 90 mg/kg, with the treatment/control ratio (T/C) value of 19.35%, 14.52% and 13.55%, respectively; tumor growth inhibition (TGI) values of 96.21%, 101.97% and 103.12%, respectively. The positive control FGF401 at 30 mg/kg had significant antitumor effect compared with the vehicle control group, with the T/C value of 15.31% and TGI value of 101.04%, measured on Day 20 after treatment; Sorafenib at 60 mg/kg had moderate antitumor effect with the T/C value of 32.75% and TGI value of 80.10%, measured on Day 20 after treatment. BLU-554 at 30 mg/kg had slight antitumor effect

with the T/C value of 68.59% and TGI value of 37.49%, measured on Day 20 after treatment. The antitumor effect of BB102 in this model was similar to that of positive control FGF401, and was significantly better than that of positive control sorafenib and BLU-554. The study 1 of "Inhibitory Effect of BB102 on the Growth of Subcutaneous Xenografts of Human Hepatocellular Carcinoma JHH-7 cells in Balb/c nude Mice" consisted of 5 groups, including the vehicle control group, positive control BB181 (FGF401-citrate) 10 mg/kg group, BB102citrate 10 mg/kg group, BB102-citrate 30 mg/kg group, and BB102-citrate 60 mg/kg group; BID, administered orally for 18 days. Compared with the vehicle control group, BB102-citrate had no significant antitumor effect at dose of 10 mg/kg; BB102-citrate had a certain antitumor effect at dose of 30 mg/kg; BB102-citrate showed significant antitumor effect at dose of 60 mg/kg. The T/C value on Day 17 of these 3 dosing groups was 94.07%, 69.75% and 46.51%, respectively; TGI value was 6.17%, 31.51% and 55.69%, respectively. Compared with the vehicle control group, positive control FGF401-citrate at 10 mg/kg had no significant antitumor effect with the T/C value of 86.61% and TGI value of 13.95% on Day 17 after treatment. The study 2 consisted of 4 groups, including the vehicle control group, positive control BLU-554 60 mg/kg group, BB102-citrate 60 mg/kg group, and BB102-citrate 80 mg/kg group; BID, administered orally for 3 weeks. Compared with the vehicle control group, BB102-citrate had a significant antitumor effect at doses of 60 mg/kg and 80 mg/kg, with T/C value of 36.07% and 20.04%, respectively, measured on Day 20 after treatment; TGI value was 66.44% and 83.10%, respectively. Compared with the vehicle control group, the positive control BLU-554 had a significant antitumor effect at a dose of 60 mg/kg with the T/C value of 43.22% and TGI value of 59.02%, measured on Day 20 after treatment. Considering the results of the two studys, BB102-citrate significantly inhibited the growth of human hepatocellular carcinoma JHH-7 cell mouse xenografts with dose dependent manner, the high dose group had the best antitumor effect, and the effect decreased along with the decrease of dose. The antitumor effect of BB102 in this model was slightly better than that of positive control BLU-554. The study of "Inhibitory Effect of BB102 on the Growth of Subcutaneous Xenografts of Human Breast Cancer MDA-MB-453 cells in B-NDG Mice" consisted of 3 groups, including the vehicle control group (BID, 22 days), BB102-citrate 80 mg/kg group (BID, 22 days), and positive control BLU-554 80 mg/kg group (BID, 22 days). The results showed that BB102-citrate 80 mg/kg had a significant antitumor effect compared with the vehicle control group with the T/C value of 28.01% and TGI value of 120.94%, measured on Day 21 after treatment. The positive control BLU-554 80 mg/kg had a significant antitumor effect compared with the vehicle control group with the T/C value of 23.01% and TGI value of 129.35%, measured on Day 21 after treatment. The antitumor effect of BB102 in this model was similar to that of positive control BLU-554. The study of "Inhibitory Effect of BB102 on the Growth of Subcutaneous Xenografts of Human Rhabdomyosarcoma SJCRH30 cells in Balb/c nude Mice" consisted of 3 groups, including the vehicle control group (BID, 22 days), BB102-citrate 60 mg/kg group (BID,

22 days), and positive control BLU-554 60 mg/kg group (BID, 22 days). The results showed that BB102-citrate had a significant antitumor effect at a dose of 60 mg/kg compared with the vehicle control group, with T/C value of 28.97% and TGI value of 76.10%, measured on day 21 after treatment. The positive control BLU-554 had a significant antitumor effect at a dose of 60 mg/kg compared with the vehicle control group, with T/C value of 28.65% and TGI value of 77.11%, measured on day 21 after treatment. The antitumor effect of BB102 in this model was similar to that of positive control BLU-554. The study of "Inhibitory Effect of BB102 on the Growth of Subcutaneous Xenograft Tumor of Human Hepatocellular Carcinoma Hep 3B cells in **CB17.SCID** Mice" consisted of 5 groups, including the vehicle control group, positive control BB181 (FGF401-citrate) 5 mg/kg group, BB102-citrate 5 mg/kg group, BB102-citrate 10 mg/kg group, and BB102-citrate 30 mg/kg group; BID, administered orally for 3 weeks. The results showed that BB102-citrate had a significant antitumor effect compared with the vehicle control group at doses of 5 mg/kg, 10 mg/kg and 30 mg/kg, with T/C values of 54.19%, 43.26% and 8.36%, respectively; TGI values of 48.51%, 60.09% and 97.04%, respectively. Positive control FGF401citrate at 5 mg/kg had a significant antitumor effect compared with the vehicle control group with the T/C value of 38.52% and TGI value of 65.11%, measured on Day 20 after treatment. The BB102-citrate significantly inhibited the growth of human hepatocellular carcinoma Hep 3B cell mouse xenografts in a dose-dependent manner: the high-dose group had the best effect, and the effect decreased with the decrease of dose. The antitumor effect of BB102 in this model was similar to that of positive control FGF401.

#### **Secondary Pharmacodynamics**

In the *in vitro* kinase selectivity study, for 207 kinases (such as FGFR4, HCK, PAK3, NEK2, MET, PIM3, FGFR1, ZAP70, AurA, etc.), 1  $\mu$ M BB102 had an inhibitory effect on FGFR4 only and the inhibition rate was up to 102.03%. However, BB102 had no inhibitory effect on the other kinases (%Inh <40%). The above results showed that BB102 has extremely high kinase selectivity, and its inhibitory activity on FGFR4 kinase is more than 400 times higher than that of other 206 kinases.

The inhibitory effect of BB102 on the proliferation of tumor cells with different expression levels of FGF19/FGFR4 was evaluated by the cell proliferation inhibition experiment. The results showed that BB102 showed a strong inhibitory effect on the proliferation of FGF19/FGFR4 high-expressing tumor cells, such as human hepatocellular carcinoma cells Hep 3B and HuH-7, human breast cancer cell MDA-MB-453, and human rhabdomyosarcoma cell SJCRH30 (IC $_{50}$  was 5.8, 8.7, 24.7 and 1.9 nM, respectively). However, BB102 showed little or no inhibitory effect on FGF19/FGFR4 low-expressing tumor cells such as human hepatocellular carcinoma cells SNU-387 and SNU-878, human rhabdomyosarcoma cell RD and human colon adenocarcinoma cell HT-29 (IC $_{50}$  of RD cell >10  $\mu$ M, and IC $_{50}$  of other cells >20  $\mu$ M).

Meanwhile, BB102 had no inhibitory effect on the proliferation of normal cells, such as mouse embryonic fibroblast NIH3T3, human umbilical vein vessel endothelial cell HUVEC, and human normal lung epithelial cell BEAS-2B ( $IC_{50}>20 \mu M$ ).

# **Safety Pharmacology**

The results of the safety pharmacology showed that BB102 was expected to have no adverse effects on the cardiovascular system, respiratory system, or central nervous system in humans. The IC50 of BB102 inhibiting the hERG current was >12 μM (maximum solubility of BB102 under test conditions) in the human embryonic kidney cell lines (hERG-HEK293) with stable expression of hERG channels. A single oral administration of BB102-citrate in Beagle dogs at doses of 40, 100 and 250 mg/kg had no significant test article-related changes in any of the evaluated cardiovascular parameters including blood pressure (systolic blood pressure, diastolic blood pressure, mean arterial blood pressure), heart rate, ECG (RR interval, PR interval, QRS duration, QT and corrected QT intervals) and body temperature. Single oral dosing with BB102-citrate up to 300 mg/kg in SD rats had no test article-related notable effects on respiratory parameters, including tidal volume, minute volume and respiratory rate. Single oral dosing of BB102-citrate to SD rats up to 300 mg/kg had no effect on the evaluated neurobehavioral parameters.

# 1.5.2 (Nonclinical) PK

# **Absorption**

Caco-2 cells permeability study: BB102-citrate was a moderate permeability compound, and it is a substrate of efflux transporters.

Single-dose and 7-day repeat-dose PK studies in SD rats: Following intravenous (2 mg/kg) and oral administration at 3 dose levels (30 mg/kg, 90 mg/kg and 270 mg/kg) of BB102-citrate in SD rats, there was no significant gender differences in drug exposure (AUClast) of BB102 in both intravenous group (the male/female ratio was 0.663) and single-dose oral groups (the male/female ratios were 0.537-0.750), while the exposure (AUClast) in males was slightly lower than that in females in repeat-dose oral groups (the male/female ratios were 0.437-0.647). Following intravenous administration of BB102-citrate at 2 mg/kg in SD rats, the AUClast of BB102 in males and females was 2194 h\*ng/mL and 3308 h\*ng/mL, respectively; BB102 was a low clearance compound in SD rats, and it was widely distributed in rat body. Following single oral administration of BB102-citrate at three dose levels (i.e., 30 mg/kg, 90 mg/kg and 270 mg/kg) in SD rats, in males, the AUClast were 27209 h\*ng/mL, 50642 h\*ng/mL and 160093 h\*ng/mL, respectively; the Cmax were 5927 ng/mL, 8460 ng/mL and 10253 ng/mL, respectively; the half-life (T1/2) were 5.18 h, 4.51 h and 6.00 h, respectively; in females, the AUClast were 36269 h\*ng/mL, 92869 h\*ng/mL and 297985 h\*ng/mL, respectively; the Cmax were 8733 ng/mL, 12067 ng/mL and 15700 ng/mL, respectively; the T1/2 were 6.47 h, 6.80 h and 5.13 h, respectively. In the dose range

of 30-270 mg/kg, in both female and male rats, the increase of  $C_{max}$  was lower than dose-proportional, while the increase of AUClast was close to dose-proportional. Following 7-day repeat oral administration of BB102-citrate at 90 mg/kg in SD rats, in males and females, the  $C_{max}$  ratios between Day 7 and Day 1 were 0.905 and 1.23, respectively; the AUClast ratios were 0.858 and 1.27, respectively, indicating that there was no obvious drug accumulation of BB102 in rats. When it was calculated using AUClast, following single oral administration of BB102-citrate at 30 mg/kg in SD rats, the absolute bioavailability of BB102 in males and females were 82.7% and 73.1%, respectively. Following oral administration of BB102-citrate at 90 mg/kg in SD rats at fasted and fed conditions, in males and females, the  $C_{max}$  ratios between fasted and fed group were 1.11 and 0.919, respectively; the AUClast ratios were 1.21 and 1.02, respectively, indicating that food had no significant effect on BB102 exposure in rats.

Single-dose and 7-day repeat-dose PK studies in Beagle Dogs: Following intravenous and oral administration of BB102-citrate in Beagle dog, the AUClast ratio between males and females was 1.00-1.34, and the  $C_{max}$  ratio between males and females was 0.983-1.38, indicating that there was no obvious gender difference for the exposure. Following intravenous administration of BB102citrate at 1 mg/kg in Beagle dogs, the AUClast of BB102 in Beagle dogs was 2040 h\*ng/mL; BB102 was a low clearance compound in Beagle dog, and it was extensively distributed in Beagle dogs. Following single oral administration of BB102-citrate at three dose levels (i.e., 10 mg/kg, 30 mg/kg and 90 mg/kg) in Beagle dog, the AUClast were 14562 h\*ng/mL, 27598 h\*ng/mL and 27415 h\*ng/mL, respectively; the Cmax were 4492 ng/mL, 8687 ng/mL and 8292 ng/mL, respectively; the  $T_{1/2}$  were 6.54 h, 6.30 h and 7.26 h, respectively. The increase of  $C_{max}$  and  $AUC_{last}$  were slightly lower than dose-proportional in the dose range of 10-30 mg/kg; however, Cmax and AUClast did not increase in the dose range of 30-90 mg/kg. It was speculated that there might be saturated absorption in the animals (Beagle dogs) in the dose range of 30-90 mg/kg. Following 7-day repeat oral administration of BB102-citrate at 30 mg/kg, the Cmax and AUClast ratios between Day 7 and Day 1 in Beagle dog were 1.07 and 1.22, respectively, indicating there was no obvious accumulation of BB102 in Beagle dog following 7-day repeat-dose at 30 mg/kg. When it was calculated using AUClast, following single oral administration of BB102-citrate at 10 mg/kg in Beagle dog, the absolute bioavailability in Beagle dog was 71.1%.

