
mg/kg/day; mild lymphoid depletion of gut associated lymphoid tissue in the ileum in females given 250 mg/kg/day; minimal atrophy of acinar cell in the mandibular salivary gland in females given ≥40 mg/kg/day; minimal epidermal atrophy and minimal adnexal atrophy in females given  $\geq$ 100 mg/kg/day. The moderate diffuse hepatocellular vacuolation in liver in females given  $\geq$  100 mg/kg/day was considered adverse. No BB102-citrate-related microscopic findings were noted at recovery sacrifice. In the 40 mg/kg/day dose group and 100 mg/kg/day dose group, the values of Cmax and AUClast in males were closed to females on Day 1 and Day 28 (Ratio: 0.704-1.16), indicating there was no significant sex differences between males and females. In the 250 mg/kg/day dose group, the AUClast on Day 1 and Day 28 and the Cmax on Day 28 in males were slightly lower than that in females (Ratio: 0.503-0.651). On Day 1 and Day 28, Cmax and AUClast did not increase significantly or decreased in both females and males in the dose range of 40-100 mg/kg/day (Ratio: 0.759-1.29). Cmax and AUClast increased in the dose range of 100-250 mg/kg/day on Day 1 and Day 28 in both females and males in a manner close to or below the dose ratio increases (Ratio: 1.07-2.50). Compared to AUClast on Day 1, no significant accumulation of AUClast was observed in females and males in the 40 mg/kg/day dose group on Day 28 (Ratio: 1.56-1.96), and accumulation was observed in females and males in the 100 mg/kg/day and 250 mg/kg/day dose groups (Ratio: 2.17-3.00). The moderate diffuse hepatocellular vacuolation in the liver in females given ≥100 mg/kg/day was considered as adverse changes. The highest nonseverely toxic dose (HNSTD) for males and females was defined as 250 mg/kg/day and 100 mg/kg/day, respectively, which corrensponded to mean Cmax and AUClast values for BB102 of 12620 ng/mL and 65467 h\*ng/mL in males, and 10166 ng/mL and 51999 h\*ng/mL in females on Day 28, respectively. The main toxic target organ was liver, and the liver related adverse changes had completely reversed during the recovery phase.

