MTD is defined as the highest dose level in which DLT occurs in  $\leq 1/6$  of the total subjects during the DLT observation period. If MTD is not reached after administration of the maximum dose level shown above, the SMC will decide whether to increase dose groups based on the nonclinical data and the efficacy doses and PK parameters of domestic and foreign similar drugs observed in human.

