#### 10.3 General Principles for Statistics

SAS® 9.4 or updated version (SAS Institute, Inc., Cary, North Carolina) will be used for statistical analysis.

Quantitative data will be described with the number of subjects of non-missing, mean, standard deviation, median, lower quartile, upper quartile, maximum and minimum.

Qualitative data will be statistically described using the number, frequency and percentage of non-missing subjects. If necessary, the two-sided 95% confidence interval (95% CI) for the percentage

Study Protocol/Version 1.0/Date: Jul 14, 2022 Confidential Page 141 of 179

will be calculated.

Baseline of safety endpoints is the most recent data prior to the first dose (data at screening are acceptable), including laboratory tests, vital signs, ECG, physical examination and ECOG score.

Prior medical history and AEs will be coded using the MedDRA (current or updated version). Previous medications and concurrent/concomitant medications will be coded according to the WHO Drug Dictionaries (current version or updated version).

Since this study is a Phase I trial, only descriptive statistics will be provided, and no hypothesis test will be performed.

Safety, PK and efficacy analyses will be performed for the dose escalation trial and expansion trial separately. In the dose escalation trial, it will be summarized overall and by dose group. In addition, it should also be summarized by gender.

The statistical analysis methods will be described in detail in the Statistical Analysis Plan.

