#### 10.4.6 PK parameters analysis

Individual concentration-time curve of BB102 (and its main metabolites, if applicable) of each subject. Moreover, mean (Mean  $\pm$  SD) concentration-time curve of BB102 (and its main metabolites, if applicable) will be plotted by dose group.

The PK parameters of BB102 (and its main metabolites, if applicable) will be analyzed using the non-compartment analysis method of the Phoenix WinNonlin 8.3.1 or updated version (Pharsight Corp., Mountain View, CA, USA) software.

For the plasma PK parameters of BB102 (and its main metabolites, if applicable), descriptive statistical analysis will be performed by dose group, with the descriptive statistics including the number of samples, mean, standard deviation, coefficient of variation, minimum and maximum. If considered necessary by the investigator and the sponsor, the linear relationship between the AUC and  $C_{max}$  of BB102 (and its main metabolites, if applicable) and dose can be analyzed.

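### The only named dose-exposure analysis is an optional linear relationship of AUC and Cmax with dose, which need not show whether exposure rises in proportion to dose

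*Protocol*

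**What the plan says.** Section 10.4.6 of the Protocol makes by-dose PK description routine: "descriptive statistical analysis will be performed by dose group", with mean concentration-time curves. Beyond that it offers one dose-exposure analysis: "If considered necessary by the investigator and the sponsor, the linear relationship between the AUC and" Cmax and dose can be analysed. Item (6) of the synopsis statistics says the same. Section 10.3 adds that "only descriptive statistics will be provided, and no hypothesis test will be performed".

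The nonclinical sections report the following:

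- **Dog, single dose (section 1.5.2):** exposure did not rise over the top dose step, and "It was speculated that there might be saturated absorption in the animals (Beagle dogs) in the dose range of 30-90 mg/kg".
- **Dog, 28 days (section 1.5.3):** Cmax and AUC "did not increase significantly or decreased in both females and males in the dose range of 40-100 mg/kg/day".
- **Rat, single dose (section 1.5.2):** the increase of Cmax "was lower than dose-proportional, while the increase of AUC last was close to dose-proportional".

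Section 4.1.1.3 names 520 and 600 mg QD as examples of added dose groups. For the case that the MTD is not reached at the top planned dose, it states: "the SMC will decide whether to increase dose groups based on the nonclinical data and the efficacy doses and PK parameters of domestic and" (the rest of the sentence refers to comparable drugs from abroad).

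**The concern.** The animal data raise a specific question: does exposure keep pace with dose? The one analysis that the protocol names is discretionary. In its plain reading it is also the wrong form, because a straight line with an intercept describes whether exposure increases, and a clear increase is compatible with exposure far below proportional.

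This matters most when added dose groups are considered. If exposure rises much less than dose, the absence of DLTs at a higher dose says correspondingly less about tolerability at a higher exposure. The protocol requires no estimate of that departure before the decision.

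**Working it through.** **1. Animal exponents.** Inputs are the single-dose means in section 1.5.2. With exposure proportional to dose^b, b = ln(exposure ratio)/ln(dose ratio).

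- Dog AUClast at 10/30/90 mg/kg was 14562/27598/27415. From 10 to 30: ratio 1.90, b = ln 1.895/ln 3 = 0.58. From 30 to 90: ratio 0.99, b about 0. From 10 to 90: ratio 1.88, b = 0.29.
- Dog Cmax was 4492/8687/8292. From 10 to 30: ratio 1.93, b = 0.60. From 30 to 90: ratio 0.95, b about 0. From 10 to 90: ratio 1.85, b = 0.28.
- Rat Cmax at 30/90/270 mg/kg was 5927/8460/10253 in males and 8733/12067/15700 in females. From 30 to 90: b = 0.32 and 0.29. From 30 to 270: ratios 1.73 and 1.80, b = 0.25 and 0.27.
- Rat AUClast was 27209/50642/160093 in males and 36269/92869/297985 in females. From 30 to 270: ratios 5.88 and 8.22, b = 0.81 and 0.96. From 30 to 90: b = 0.57 and 0.86. From 90 to 270: b about 1.05 and 1.06.

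The plan's description is therefore reproduced: a dog plateau from 30 to 90 mg/kg, flattened rat Cmax, and rat AUC close to proportional.

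**2. Where this lies on the human scale.** Section 4.1.1.1 converts by dose/36.88 × km × 60, with km 21.47 for dog and 6.60 for rat. As a check, 40/36.88 × 21.47 × 60/5 = 279.4, the figure printed there. Without the safety factor:

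- dog 10/30/90 mg/kg = 349/1048/3144 mg/day;
- rat 30/90/270 mg/kg = 322/966/2899 mg/day.

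The dog plateau starts at about 1048 mg/day. The segments 349 to 1048 (dog, b about 0.6) and 322 to 966 (rat Cmax, b about 0.3) contain 420, 520 and 600 mg. If such an exponent applied in patients, going from 420 to 600 mg (ratio 1.43) would raise exposure by a factor of 1.43^0.6 = 1.24 or 1.43^0.3 = 1.11.

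**3. What a straight line shows.** For exposure = dose^b without noise at 50, 100, 160, 240, 320 and 420 mg (an 8.4-fold range), the straight-line R² is 0.986 at b = 0.58 (exposure rises 3.4-fold), 0.980 at b = 0.5 (2.9-fold) and 0.960 at b = 0.3 (1.9-fold).

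**4. Simulation.** It used 4,000 trials per scenario, 1+3+3+3+3+3 = 16 fasted subjects and log-normal error. The protocol gives no between-subject CV, so 30% and 50% are assumed (shown as 30% / 50%). The line is counted as looking straight when its slope is significant and a quadratic term is not. This measures how the fit would look; it is not a rule in the protocol.

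| True shape | Line looks straight | Power-model 90% CI for b wholly below 1 |
|---|---|---|
| b = 1 | 94% / 91% | about 5% / 5% |
| b = 0.8 | 93% / 83% | 49% / 25% |
| b = 0.58 | 91% / 62% | 95% / 66% |
| b = 0.5 | 87% / 50% | 99% / 78% |
| b = 0.3 | 52% / 24% | 100% / 97% |
| proportional, then flat from 240 mg | 49% / 51% | 63% / 35% |

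At b = 0.58 and CV 30% the straight-line picture (91%) is almost the same as under true proportionality (94%). The power model separates the two (95% against about 5%).

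**The case against.** The strongest reply is that regression form is ordinary SAP content. Section 10.3 defers detail to the SAP, which is not at hand. The wording does not say untransformed, and it may be loose language for dose linearity; a power model is itself linear on the log scale. This stands in part. A SAP could settle the form, but the protocol itself names the relationship and makes it discretionary in two places.

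Second, flat exposure would not go unseen. By-dose descriptive PK is mandatory, section 4.1.1.6 puts PK before the SMC, and section 4.1.1.3 allows escalation to be adjusted on PK. A severe plateau also fits a line poorly: the dog means give R² = 0.47 for AUC and 0.40 for Cmax. A fitted intercept can reveal the departure too, being significant in 58% / 26% of runs at b = 0.58. These points stand. What is missing is a required estimate, not every chance of noticing.

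Third, the power model is weak for mild departures and for a late plateau, as the table shows. That also stands and shapes the fix.

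A reader might infer more than the documents support:

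- **Flattening in both species generally.** Rat AUC was close to proportional overall, and one 28-day male rat AUC ratio was 4.32 for a 3-fold dose.
- **A dog plateau inside the planned range.** By conversion it lies above 600 mg, and the 28-day flat range of 40 to 100 mg/kg/day converts to 1397 to 3493 mg/day.
- **A significant slope taken as proof of linearity.** No passage says so, and hypothesis tests are excluded.
- **Expansion doses compared as if they differed in exposure.** No such comparison is planned.

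**Conclusion.** The point holds in a limited form. The protocol's own data suggest sub-proportional exposure over segments that, by its own conversion, cover 420 to 600 mg. Its one dose-exposure analysis is optional and, read as a straight-line fit, does not estimate departure from proportionality. In that reading, exposure at exponent 0.5 to 0.6 would usually look linear at CV 30%, and in about half to 62% of trials at CV 50%.

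This rests on three assumptions: body-surface conversion, animal exponents as a guide to the human range, and the assumed CVs. None of it shows that exposure in patients will saturate, or that the SMC would overlook it if it did. It is a worthwhile correction to the analysis text, not a flaw in the design.

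**What to change.** Replace the optional sentence in section 10.4.6 and in item (6) of the synopsis statistics by a routine estimation analysis, for example:

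*Dose proportionality of single-dose AUC0-inf, AUC0-t and Cmax, and of AUCss and Css,max, in the fasted groups will be estimated with the power model ln(parameter) = a + b × ln(dose). The exponent b will be reported with its 90% CI, together with dose-normalised exposure by dose group.*

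The dose-normalised summaries are needed because, with about 16 subjects, b alone is weak for mild departures or a late plateau; b should be read as an estimate with its interval. Include both in the PK data that the SMC already reviews when it considers additional dose groups.

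This adds no hypothesis test, no dose rule and no sampling. The cost is one regression per parameter and a wording change in the protocol and SAP.
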